VIE SCOPE VERSUS MACINTOSH LARYNGOSCOPE IN EXPECTED EASY AIRWAYS: A RANDOMIZED CONTROLLED TRIAL

NCT NUMBER:
NCT06149338

21/08/2024

STUDY PROTOCOL

Ethics

The study protocol was approved by the Scientific Committee (approval number: 141/09.07.2023). Since the strategies employed in both study groups are considered components of standard care, and the study involved patients undergoing elective and nonelective surgery or being treated in the emergency settings, the committee waived the necessity for written informed consent. The study was registered on ClinicalTrials.gov (NCT06149338) on 04.01.2024 and was in accordance with the principles of the Declaration of Helsinki and Good Clinical Practice guidelines.

Study design

A prospective, randomized, single-blind, superiority, clinical trial has been conducted since 26.01.2024. The intubations were performed by the same resident of anesthesiology, who had already completed successfully at least 50 intubation attempts with each one of the two examined laryngoscopes, before the beginning of the patient enrollment into the study, in order to eliminate any impact from a different learning curve of any laryngoscope and to gain competency, although concurrently there are limited data for Vie Scope, fostering its short learning curve, despite the mentioned necessity of previous practice with straight blade devices. Every intervention was made under the supervision of an experienced Anesthesiologist consultant. In case of certified or possible COVID-19 infection of the patient, the airway operator was instructed to use the required PPE.

The current study included patients of both sexes. Apart from the gender, the age (\geq 18 years old) and the Body Mass Index (B.M.I.: 18.5 – 30 kg/m²) were considered as inclusion criteria of this study. A positive or negative rapid test for COVID-19 or possible contamination of the patient was documented as well, without affecting the patient's eligibility for the study inclusion. Also, every patient underwent an adequate airway assessment, including airway history and physical examination, preoperatively or in the emergency settings, when feasible, to distinguish the patients with anticipated easy airways management. The chin protrusion (upper lip bite test), the thyromental distance and the Mallampati score were mostly evaluated, due to their efficacy in detecting an anticipated difficult airway. Consequently, the higher a patient could bite the upper lip with the lower incisors, the thyromental distance > 3 ordinary fingerbreadths and the Mallampati scores 1, 2 were positive predictive factors of an expected easy airway. Despite the high sensitivity of the upper lip bite test, the low sensitivities of other tests, such as the Mallampati score, and the confined airway assessment in emergency settings or patient cooperation necessitated the adoption of the Cormack - Lehane classification as a recruitment criterion of this study. According to this scale, the glottis visualization grades 1, 2a, 2b, after direct laryngoscopy, were compatible with easy endotracheal intubation, making these patients eligible participants in the present study. In contrast, patients with age under 18 years old, with BMI under 18.5 kg/m² and over 30 kg/m², inability to bring mandibular incisors anterior to maxillary incisors, thyromental distance < 3 ordinary

fingerbreadths, Mallampati scores 3, 4 and Cormack - Lehane classification grades 3 and 4 were excluded from this clinical trial.

The randomization of the patients was generated immediately before the anesthesia induction, after the investigator Anesthesiologist trainee was assigned to the patient, either in the operating room or in the emergency settings, using sealed opaque envelopes, that contained demographic data and medical background of the participants in pseudonymized form. The allocation ratio was 1:1 to either Vie Scope or Macintosh laryngoscope. The patients remained blinded to the intervention procedure, while this was not feasible for the airway operator, due to the study's nature.

Patients, being randomized into the intervention group, underwent direct laryngoscopy and subsequent intubation attempt with the Macintosh laryngoscope (HEINE Optotechnik GmbH & Co. KG, Gilching, Germany), (Figure 1). The size of the blade (3 or 4) was chosen at the discretion of the Anesthesiologist trainee. The airway operator implemented the midline approach for the displacement of the tongue from the area of view and placed the tip of the Macintosh blade in the epiglottic vallecula, so as to achieve the indirect elevation of the epiglottis and exposure of the vocal cords, followed by the endotracheal intubation.

Patients, being randomized into the control group, received direct laryngoscopy and ensued intubation attempt with the Vie Scope® (Adroit Surgical LLC, Oklahoma City, OK, USA) (Figure 2). The introduction of the Vie Scope into the patient's mouth could be performed by either of the mouth corners, according to the patient's anatomical characteristics. The gentle back tilt of the head was followed by the application of the paraglossal or retromolar approach, for aligning the oral, pharyngeal and laryngeal axis. After its forwarding, until the glottis was visualized, by elevating directly the epiglottis, a 15 Fr bougie with colorful bands, the VOIR Bougie (Adroit Surgical LLC, Oklahoma City, USA), was introduced appropriately endotracheally, through the cylindrical lumen of the intubation channel of the Vie Scope. The careful removal of the Vie Scope was followed by the endotracheal tube (ETT)'s railroading over the bougie. As soon as the ETT was positioned, the bougie was removed too.

After the tube's cuff was inflated, until there was no air leak from the trachea, the correct ETT's placement was verified in both groups by the patient's ventilation. The choice of the size and the type of the ETT was at the discretion of the airway operator. In addition, the laryngeal view was estimated, under direct laryngoscopy with each laryngoscope, according to the Cormack - Lehane grading system. The airway operator was prompted to perform any external laryngeal manipulation, such as the backward, upward, rightward pressure (BURP), or to use any assistant equipment, like bougies, stylets, forceps, lubricant gel or spray, for optimizing the laryngeal view and facilitating the intubation process. The supervisor consultant would be involved in case of two failed intubation attempts by the trainee, or whenever the situation required the intervention of an experienced Anesthesiologist.

Outcome measures

The primary outcome measures were the first attempt intubation success rate and the required mean intubation time. The intubation time was defined as the time interval from the insertion of the laryngoscope into the patient's mouth, until the inflation of the ETT's cuff of each patient.

Contrarywise, the overall intubation success rate and the glottis visualization, based on the Cormack - Lehane classification, were regarded as the secondary outcomes.

STATISTICAL ANALYSIS

The statistical analysis was performed with SAS version 9.4 (SAS Institute, Cary, NC, USA) along with Microsoft Excel 2007 for data collection. For the descriptive statistics, quantitative variables were presented as means and standard deviations (SD) as well as using medians and quartiles 1 and 3 (Q1 and Q3 respectively). Qualitative variables were presented using the relative frequencies and the relevant percentages. For the inferential part of the analysis, the Kruskal – Wallis test was applied for the analysis of numerical data, because they did not follow a normal distribution, according to the Kolmogorov - Smirnov test, while the χ^2 test and, if required, the Fisher's exact test were performed for the categorical data. All tests were two-sided, the confidence intervals (CIs) were determined as 0.95 and thus significance cut-off level was for $p < 0.05$.

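### Cormack-Lehane grade 3/4 is an exclusion judged at laryngoscopy, which on the natural reading follows randomisation, and no analysis set keeps those patients in

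*Combined protocol and SAP*

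**What the plan says.** All of the eligibility text is under Study design.

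- **Bedside assessment.** Airways are assessed "preoperatively or in the emergency settings, when feasible, to distinguish the patients with anticipated easy airways management".
- **Why the Cormack-Lehane (CL) grade was added.** The low sensitivity of some bedside tests and the limits of emergency assessment "necessitated the adoption of the Cormack - Lehane classification as a recruitment criterion of this study".
- **Inclusion.** The plan states that "the glottis visualization grades 1, 2a, 2b, after direct laryngoscopy, were compatible with easy endotracheal intubation, making these patients eligible participants".
- **Exclusion.** Patients with "Mallampati scores 3, 4 and Cormack - Lehane classification grades 3 and 4 were excluded from this clinical trial".
- **Randomisation.** "The randomization of the patients was generated immediately before the anesthesia induction".
- **Laryngoscopy.** Patients allocated to Macintosh "underwent direct laryngoscopy and subsequent intubation attempt with the Macintosh laryngoscope"; patients allocated to the other device "received direct laryngoscopy and ensued intubation attempt with the Vie Scope".

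Outcome measures lists CL grade as a secondary outcome beside overall success. First-attempt success and mean intubation time are primary. Statistical analysis names no analysis population.

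The plan does not state when, with which device or by whom the eligibility grade was recorded, whether this was before or after manoeuvres to improve the view, or whether any randomised patient was removed.

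**The concern.** A grade that needs direct laryngoscopy cannot normally be known before induction, and allocation is fixed before induction. Followed as written, the rule therefore removes patients after randomisation.

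The device can affect the grade. With Macintosh the tip is placed "so as to achieve the indirect elevation of the epiglottis and exposure of the vocal cords", whereas the Vie Scope lifts the epiglottis directly. The operator knows the allocation. If the operator also assigns the eligibility grade, which the plan does not say, exclusion is decided with knowledge of the arm.

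Those removed have the worst view, and are plausibly the likeliest to fail the first attempt or take longest. The arm that loses more of them looks better than it is. First-attempt success, time and overall success can be biased in either direction. The CL outcome is truncated to the extent that grade 3/4 patients are removed, and completely if all are.

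**Working it through.** **Order of events.** Bedside assessment comes first, then randomisation just before induction, then laryngoscopy with the allocated device, then intubation. No screening laryngoscopy before allocation is described. The plan provides for view-improving manoeuvres and for the consultant after two failed attempts, but does not say whether a patient then found to be grade 3/4 stays in the analysis.

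**Inputs.** The documents give no grade 3/4 rate, success rate, time or sample size, so there is no planned figure to reproduce. Every value below is an assumption.

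**First-attempt success.** Let S be success in all randomised patients of an arm, p the share removed and q the success among those removed. Success in the retained set is (S − p·q)/(1 − p).

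Example with S = 90% in both arms and q = 40%: at p = 10%, (0.90 − 0.04)/0.90 = 95.56%; at p = 2%, (0.90 − 0.008)/0.98 = 91.02%. The gap is 4.54 points where the truth is zero.

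| Removed, one arm v the other | Gap, q = 40% | Gap, q = 60% |
|---|---|---|
| none, or equal | 0 | 0 |
| 2% v 1% | 0.52 | 0.31 |
| 4% v 1% | 1.58 | 0.95 |
| 6% v 2% | 2.17 | 1.30 |
| 8% v 2% | 3.33 | 2.00 |
| 10% v 2% | 4.54 | 2.72 |

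Three variants:

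- *Equal removal, but q = 40% in one arm and 60% in the other.* The gap is 0.20·p/(1 − p), which is 0.20, 0.41, 1.05 and 2.22 points at p = 1, 2, 5 and 10%.
- *True 92% v 88%.* With equal p and q the 4 points become 4/(1 − p): 4.04, 4.08, 4.21 and 4.44 at the same p. With 2% and 1% removed, the result is 4.37–4.58 if the better arm loses more and 3.55–3.75 if it loses fewer. With 10% and 2% removed, it is 6.98–8.80 or −0.27 to 1.54.
- *Device acts only through the view, with 95% success in grades 1–2b in both arms.* The true difference in all randomised patients is (difference in p)·(0.95 − q): 0.35–0.55 points at 2% v 1%, and 1.05–4.40 at 4% v 1% to 10% v 2%. After exclusion it is exactly 0.

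**Mean time.** Set the overall mean to 1 in both arms and the mean of the removed to k. The retained mean is (1 − p·k)/(1 − p). For k = 1.5 to 2 the gap is 0.52–1.03% of the mean at 2% v 1%, and 1.58–9.07% at 4% v 1% to 10% v 2%.

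**Rank test.** Take one common time distribution, with u the mean percentile of removed patients. If arms A and B lose pA and pB, the chance that a retained B patient is slower than a retained A patient is [0.5 − pA(1 − u) − pB·u + 0.5·pA·pB]/[(1 − pA)(1 − pB)]. For u = 0.75 and 0.90 this gives 0.5026 and 0.5041 at 2% v 1%, 0.5079 and 0.5126 at 4% v 1%, and 0.5227 and 0.5363 at 10% v 2%. It is 0.500 when removals are equal.

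**If outcomes of removed patients cannot be recovered.** Best/worst-case bounds on the success difference have width pA + pB: 3 points at 2% v 1%, and 5 to 12 points from 4% v 1% to 10% v 2%.

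**The case against.** The timing is inferred. Calling the grade a recruitment criterion is pre-enrolment language, and the criteria are set out before the randomisation paragraph. Airway history is part of the assessment, so a grade from an earlier anaesthetic is possible. This cannot be ruled out. It fits poorly, however, with adopting the grade because emergency assessment is limited, where an old record is least likely to be at hand. Even on that reading the timing, device and assessor are unstated.

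The plan also says that the view was graded with each laryngoscope. If every patient was graded with both devices and one common grade decided eligibility, removal need not differ by arm. The wording is ambiguous, but the arm descriptions give each patient only the allocated device.

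Harm is conditional, since no document reports a removal. The larger figures need 10% v 2% removed, and prior screening on lip bite, thyromental distance, Mallampati score and BMI should make grades 3/4 less common, although airway assessment was done only when feasible. At 2% v 1% the effect is small. All of this stands. It limits what can be said about size, but does not supply the missing rule for patients randomised and then graded 3 or 4.

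Finally, keeping such patients sets aside a stated exclusion. In a trial of expected easy airways that is defensible, because expectation is formed before laryngoscopy, but the eligibility text must then be amended to match.

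**Conclusion.** The concern holds, and must be settled before the results are interpreted. Confidence is high about what the plan states and omits; there is no claim that removals occurred.

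There is no bias if nobody was removed or, when there is no true difference, if removals match in number and outcome. Otherwise the bias runs from a fraction of a point at low removal rates to one that could hide or reverse a 4-point true difference at 10% v 2%. Its direction depends on which arm loses more patients. The documents give no means of telling which case applies.

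**What to change.** 1. State when, with which device and by whom the eligibility grade was taken, and whether before or after view-improving manoeuvres. Report from the randomisation list the number removed per arm for grade 3/4, including zero.
2. Whatever the answer, define the primary analysis as all randomised patients in their allocated arm regardless of CL grade, for both primary and both secondary outcomes, with CL reported over all grades.
3. Only if randomised patients were removed, restore them. Where data cannot be recovered, give best/worst-case bounds: all successes or all failures for the two success rates, and best or worst rank for time. The mean has no worst case unless a cap is stated. CL needs no bound at the 1–2b v 3/4 level only if the removal grade came from the allocated device.
4. For patients not yet enrolled, if any, base eligibility only on information available before the envelope is opened.
5. Keep the grade 1–2b set only as a labelled sensitivity analysis.

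**Cost.** If the count is zero or the grade predates randomisation, steps 1, 2 and 5 need only wording and a count, and nothing more is needed for patients already enrolled. If patients were removed, records must be recovered, and some may not exist. Statistical analysis already reports a normality result, so some analysis appears to have been done and a re-analysis would then be needed. Enrolment began on 26.01.2024 and the document is dated 21/08/2024, so step 4 cannot reach patients already enrolled. The downside is that a few airways that proved difficult stay in the expected-easy population.

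### Two primary outcomes are each tested at two-sided 0.05 with no success or multiplicity rule, so the error rate of the superiority claim is undefined (up to about 10% if either outcome suffices)

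*Combined protocol and SAP*

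**What the plan says.** - **Outcome measures** lists the primary outcomes without ranking them: "The primary outcome measures were the first attempt intubation success rate and the required mean intubation time". The word joining them makes a list; it does not define success.
- **Statistical analysis** sets the only error criterion: "All tests were two-sided, the confidence intervals (CIs) were determined as 0.95", with "significance cut-off level was for $p < 0.05". This is a per-test level, and no overall level is given.
- **Statistical analysis** assigns Kruskal–Wallis to numerical data and chi-square, or Fisher's test where needed, to categorical data. One primary outcome therefore falls under each method.
- **Study design** states the objective: "A prospective, randomized, single-blind, superiority, clinical trial has been conducted since 26.01.2024". It names neither the device expected to be superior nor the outcome that decides.

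The document contains no testing order, alpha split or multiplicity adjustment. The outcome and analysis sections are continuous prose, with no sign that text was removed at this point.

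**The concern.** With two primary outcomes and no decision rule, a reader cannot tell in advance which results count as success. The same data could be reported as a positive trial (one outcome significant) or a negative one (not both significant), and the plan would support either report.

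If significance on one outcome is taken as superiority, the trial has two full-alpha chances at its main claim.

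The outcomes could also point in opposite directions. In the Vie Scope arm a bougie is placed and the tube is then railroaded over it, and the clock runs until the cuff is inflated. Time and first-attempt success therefore need not favour the same device. The plan does not say what would be concluded in that case.

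**Working it through.** **Inputs from the document.** Two primary outcomes (Outcome measures); two-sided 0.05 for each test (Statistical analysis); superiority objective with no favoured device (Study design). The plan states no family-wise error, sample size, power or success rate, so it has no design figure to reproduce. Its only error figure is internally consistent: 1 − 0.95 = 0.05.

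**1. Either outcome suffices, no true difference on either.**
- Independent tests: 1 − (1 − 0.05)² = 1 − 0.9025 = 9.75%.
- Upper bound under any dependence, if each test holds its level: 0.05 + 0.05 = 10%.
- Correlated tests, using P(|Z₁| > 1.96 or |Z₂| > 1.96) for a bivariate normal. The correlations are assumed:

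| Correlation | Error, either suffices | Error under Holm |
|---|---|---|
| 0 | 9.75% | 4.94% |
| 0.3 | 9.51% | 4.84% |
| 0.5 | 9.07% | 4.65% |
| 0.7 | 8.35% | 4.30% |
| 0.9 | 7.04% | 3.62% |

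With both nulls true, Holm errs when the smaller p-value is below 0.025. At zero correlation that is 1 − 0.975² = 4.94%.

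**2. Both outcomes required.** The error is at most 5%. With both nulls true it is 0.05² = 0.25% if the tests are independent, and 0.93% at a correlation of 0.5.

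**3. Allowing for the discrete binary test.** Exact binomial enumeration was used for first-attempt success: Fisher's test if an expected count is below 5, otherwise uncorrected chi-square. This was combined with an independent time test at 5%. Success rates and arm sizes are assumed. Either-outcome error:

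| Per arm | 80% success | 90% | 95% | 98% |
|---|---|---|---|---|
| 50 | 9.95% | 8.86% | 5.84% | 5.03% |
| 100 | 9.88% | 9.93% | 8.11% | 5.45% |
| 200 | 9.83% | 9.58% | 9.57% | 7.26% |

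The size of the binary test alone follows from 1 − (1 − error)/0.95. At 50 per arm and 95% success this is 1 − 0.9416/0.95 = 0.9%, so the test contributes little. At 50 per arm and 80% success it is 1 − 0.9005/0.95 = 5.2%, because uncorrected chi-square runs slightly over its level there.

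**4. Power cost of the remedies.**
- A test at two-sided 0.025 has critical value 2.241 instead of 1.960. From 80% power at 0.05: Φ(1.960 + 0.842 − 2.241) = 71.2%. From 90%: Φ(1.960 + 1.282 − 2.241) = 84.1%.
- Holm recovers a little even when the other null is true (independent tests): 0.712 + 0.025 × (0.80 − 0.712) ≈ 71.5%. The same step gives 84.3% from 90%.
- Sample-size ratio to restore power at 0.025: [(2.241 + 0.842)/(1.960 + 0.842)]² = 1.21 for 80%; [(2.241 + 1.282)/(1.960 + 1.282)]² = 1.18 for 90%.
- Both required, independent tests: 0.8² = 64%, or 0.9² = 81%.

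**The case against.** **The plan never says that one outcome is enough.** This is true. If both were meant to be required, no alpha adjustment is needed. What the document shows is an undefined rule, and 10% is the bound under one reading of it. The rule still has to be written, because the text supports neither reading.

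**In this population the inflation may be small.** Entry is restricted to expected easy airways, and "Cormack - Lehane classification grades 3 and 4 were excluded from this clinical trial". High first-attempt success is therefore plausible. At 95–98% success the either-outcome error is 5.0–5.8% with 50 per arm and 5.5–8.1% with 100 per arm. This stands as a limit on size. With 200 per arm at the same rates it is 7.3–9.6%, and the document does not show which case applies.

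**The outcomes are probably dependent.** A failed first attempt is likely to lengthen the recorded time, and the enumeration above treats the time test as independent. Positive dependence would lower those figures by an unknown amount. In the normal approximation the error is still 7.04% at a correlation of 0.9.

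**The near-10% figure counts false findings for either device.** In one named direction it is 1 − 0.975² = 4.94% against a nominal 2.5%. The near-doubling is the same. The two-directional figure suits a plan with two-sided tests and no favoured device.

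**It may be too late to pre-specify a rule.** The analysis text is in the past tense and already reports a distributional result for the numerical data: "because they did not follow a normal distribution, according to the Kolmogorov - Smirnov test". A rule written now may not count as pre-specified. This weakens the remedy but does not remove the need for one.

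**Holm is only one of several valid choices.** A fixed testing order, 0.025 for each outcome, or a both-required rule would also close the gap.

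**Conclusion.** The concern holds. The plan gives two primary outcomes a full 5% each and does not define success, so the error rate of the superiority claim lies anywhere from at most 5% (both required) to about 10% (either suffices). The 9.75% figure assumes an either-outcome rule, independent tests, and tests that hold their nominal level. Correlation, conservative exact testing and near-ceiling success would each reduce it, in some assumed settings to about 5%. Those factors affect the size of the inflation; they do not supply the missing rule. This should be corrected, because it concerns the trial's central claim and is cheap to fix, but its severity depends on a rule the plan leaves unstated.

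**What to change.** Add one of these rules to the Statistical analysis section.

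*Preferred:* The two primary outcomes are tested by Holm's procedure at an overall two-sided alpha of 0.05: the smaller p-value is compared with 0.025 and, if significant, the other with 0.05. Superiority is claimed only for the specific outcome that is significant under this rule. If the outcomes favour different devices, this is reported as such and not as overall superiority.

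*Alternative, if that was the intent:* Superiority is claimed only if both primary outcomes are significant at two-sided 0.05 in favour of the same device.

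Holm is valid under any dependence between the outcomes, so no correlation has to be assumed. If outcome data had been examined before the rule is written, the rule should be labelled post hoc.

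**Cost.** A few sentences; no new data or patients. Under Holm, when only one outcome truly differs, 80% power becomes about 71% and 90% becomes about 84%. Restoring it would take about 21% or 18% more patients. The both-required rule costs more: 64% or 81% joint power for two independent tests with 80% or 90% each.

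### Is intubation time, a primary outcome, left undefined when attempts are repeated or the patient is never intubated?

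*Combined protocol and SAP*

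**What the plan says.** Outcome measures names two primary outcomes: "The primary outcome measures were the first attempt intubation success rate and the required mean intubation time". Its definition of the second is: "the time interval from the insertion of the laryngoscope into the patient's mouth, until the inflation of the ETT's cuff of each patient". Overall success and glottic view are secondary.

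The description of the intubation procedure, just before Outcome measures, allows for repeat attempts and for a senior anaesthesiologist to step in: "The supervisor consultant would be involved in case of two failed intubation attempts by the trainee, or whenever the situation required the intervention". It also puts confirmation of tube position, by ventilating the patient, after inflation: "After the tube's cuff was inflated, until there was no air leak from the trachea, the correct ETT's placement was verified in both groups".

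Statistical analysis summarises times in two ways: "quantitative variables were presented as means and standard deviations (SD) as well as using medians and quartiles 1 and 3". It tests them with Kruskal-Wallis, "because they did not follow a normal distribution, according to the Kolmogorov - Smirnov test". It gives no rule for missing or worst-rank times.

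The Study design text restricts the trial to expected easy airways ("Mallampati scores 3, 4 and Cormack - Lehane classification grades 3 and 4 were excluded from this clinical trial"). All intubations are done by one trainee with at least 50 prior successes on each device.

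**The concern.** Neither the insertion nor the inflation is qualified as first, last or successful. With a single attempt this is harmless. With two or more, at least three quantities fit the words: total elapsed time, the time of the successful attempt, and a time only for patients whom the trainee intubated. A patient who is never intubated has no end point at all, so strictly the arm mean does not exist.

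The readings answer different questions. Timing only the successful attempt, or leaving out patients without a time, conditions on success. Success may differ by device and is itself the other primary outcome. A device that fails more often could then look as fast as its comparator. The named outcome is the mean, which is the summary most sensitive to a few long times. The operator is unblinded and no separate timekeeper is named, which makes an unstated rule less comfortable.

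**Working it through.** The documents give no failure rate, SD, sample size or effect size for time, so there is no figure of the plan's own to reproduce. The check has two parts: what the wording already settles, and how far the choice of reading could move the result under assumed inputs.

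**What the wording settles**

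- *Repeat attempts.* The interval is defined once per patient. First insertion to final inflation is the plain way to apply it, and failed attempts then count against the allocated device.
- *Takeover.* A patient intubated by the consultant has an insertion and a cuff inflation, so the definition yields a time. What is unstated is whether the consultant's part counts. Analysing patients as randomised would include it.
- *Never intubated.* This is the only case with no value. The number of such patients follows from the overall success rate, a planned outcome.

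**Effect of the reading on the mean and the test**

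Assumed: successful-attempt times equal in both arms (mean 25 s, SD 8 to 10 s), and each first-attempt failure adds E = 40 s (25 + 15) to 90 s (60 + 30). The difference in mean elapsed time is (fB − fA) × E. If only the successful attempt is timed, it is 0 s. Kruskal-Wallis rejection comes from 2,000 simulations at an assumed 100 per arm.

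| First-attempt failure | Mean difference, elapsed time | Rejection, elapsed time | Rejection, successful attempt only or first-attempt failures dropped |
|---|---|---|---|
| 2% vs 5% | 0.03 × 40 = 1.2 s to 0.03 × 90 = 2.7 s | 5.8–7.2% | 4.4–5.4% |
| 5% vs 10% | 0.05 × 40 = 2.0 s to 0.05 × 90 = 4.5 s | 9.0–11.0% | 4.4–5.4% |
| 5% vs 15% | 0.10 × 40 = 4.0 s to 0.10 × 90 = 9.0 s | 21.8–24.2% | 4.4–5.4% |

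The median moves less. If every first-attempt failure is ranked last, an arm's median is the log-normal quantile at 0.5/(1 − f). The between-arm difference then shifts by 0.30–0.37, 0.57–0.69 and 1.22–1.48 s in the three rows. That overstates the issue, because a patient intubated at the second attempt does have a time.

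**Effect of a special rule for takeovers and the never intubated**

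Assume that takeover follows two failures and that attempts are independent. The fraction concerned is then f²: 0.02² = 0.04%, 0.05² = 0.25%, 0.10² = 1.00% and 0.15² = 2.25%. Kruskal-Wallis rejection with 100 per arm, SD 9 s, 65 s added and 2,500 simulations:

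| First-attempt failure | Elapsed time for all | Two-failure patients ranked worst | Two-failure patients dropped |
|---|---|---|---|
| 2% vs 5% | 6.2% | 6.2% | 6.2% |
| 5% vs 10% | 9.3% | 9.4% | 9.6% |
| 5% vs 15% | 23.1% | 23.9% | 16.3% |

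The simulation error in the last row is √(0.231 × 0.769 / 2,500) = 0.8 percentage points, so ranking these patients worst cannot be told apart from using their elapsed time. Dropping them matters only in the last row, and the definition does not support dropping patients who have a time.

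**The case for a change.** The strongest case is that the reading can decide the direction of the result. Another set of assumptions has Vie Scope 4 s slower at the median (29 s against 25 s), a failed attempt with median 45 s, a 30 s gap, 60 s more at takeover, and 100 per arm. With failure per attempt of 5% on Vie Scope and 20% on Macintosh, the mean difference (Vie Scope minus Macintosh) is −11.5 s from first insertion to final inflation, but +4.3 s for the last attempt alone. At 5% against 10% it is −0.5 s against +4.3 s, with rejection of 45% against 83%. One sentence of definition would remove the doubt.

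The arithmetic stands, and so does the point that the rule is not written down. Three things limit it.

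- The reversal needs a less natural reading and a wide gap in failure rates. The documents give no reason to expect that gap in selected easy airways with a practised operator. With 5% failure in both arms the mean difference is about the same on every reading, although rejection in the 4 s setting is 73% on elapsed time and 82% on the last attempt.
- A gap in failure of that size would appear directly in first-attempt success, the other primary outcome, so failures would not be hidden.
- Elapsed time is not plainly better than attempt time. It includes pauses and consultant work, and it partly counts first-attempt failure again. The choice is to some extent a preference.

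It is also true that a misplaced tube could stop the clock if the definition is read literally. That would bias the comparison only if misplacement differed by arm, which the documents do not show.

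**Conclusion.** No change to the plan follows. This is missing detail that an analyst would fill sensibly: one interval per patient, from first insertion to final inflation, with takeovers kept in the allocated arm. Any patient never intubated would be counted beside the mean and, in a rank test, naturally placed last.

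Under the assumed inputs, the gap between this reading and the least favourable one runs from 1.2 s to 9.0 s in the mean. Rejection on this reading is about 6–7% to 22–24%, against about 5% on the other. A separate worst-rank rule adds at most 0.8 percentage points. All of this rests on assumed failure rates, times and sample size. If takeover often came before two failures, which the procedure allows, the fraction affected would be larger than f².

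Enrolment has run since 26.01.2024, and Statistical analysis already reports the outcome of a normality test. If the data have been examined, a rule written now would be post hoc. Saying in the results which interval was measured is ordinary reporting.
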